### 12.6. Study Drug Accountability

The Investigator or designee must maintain accurate records of the receipt of all study drug, including date received, lot number, expiration date if applicable, amount received, condition of the package and the disposition of all study drug.

Patients will be instructed to bring their bottles, whether empty or containing unused study medication, with them for a compliance assessment during each clinic visit. Compliance will be assessed via tablet counts. Details of study medication compliance will be recorded on the eCRF. Investigational drug orders, records of receipt, dispensing records, and inventory forms will be examined and reconciled during and at the end of the study. Both the investigational drug that was used during the course of the study, as well as any remaining unused investigational drug, will be accounted for on a drug accountability record provided to the Investigator by Processa or its designee. In addition, a copy of all completed drug accountability records will be retained in the Investigators' Study Files, with a copy sent to Processa. The investigational drug will be kept in a locked area with limited access under controlled room temperature conditions.

### 12.7. Study Drug Handling and Disposal

Investigational drug orders, records of receipt, dispensing records and inventory forms will be examined and reconciled during and at the end of the study. Unless otherwise directed, at the end of the study, all unused and partially used containers of investigational drug must be returned as designated by the Sponsor.

In addition, a copy of all completed drug accountability records must be retained in the Investigators' Study Files, with a copy sent to the Trial Master File. The investigational drug shall be kept in a locked area with limited access under controlled room temperature conditions (see Section 12.3).

### 13. Demographics and Other Baseline Characteristics

Subject demographic characteristics (e.g., age, sex, and race) and baseline characteristics will be collected. Relevant NL-related as well as general medical history/current medical condition data until the start of study treatment will be collected, such as date of diagnosis of NL, previous treatments for NL, other skin disease history, and diabetic status.

### 14. ASSESSMENT OF EXPLORATORY EFFICACY

### 14.1. Exploratory Efficacy Variables

#### 14.1.1. Investigator Global Assessment: Necrobiosis Lipoidica (IGA:NL)

The Investigator Global Assessment: Necrobiosis Lipoidica (IGA:NL) is a tool that has been adapted to assess the presence and severity of necrobiosis lesions. Adaptation of the scale was based on input from 4 dermatologists with expertise in granulomatous disorders, NL, and ulcers. The scale has face validity and has performed well in limited testing. The scale scores activity based on features of inflammation/erythema, induration, and ulceration (Table 3) and damage based on features of pigmentation, scarring, and atrophy (Table 4). Further validation of the scale is ongoing.

Instructions: Select (1) a numeric score that describes the activity and (2) a numeric score that describes the damage of the reference lesion\*. (\*Reference lesion is the most severely affected lesion.)

Table 3: IGA:NL Activity

Score	Definition	Description
0	Clear	No inflammation, induration or ulceration, but residual damage may be present.
1	Almost Clear	Minimal inflammation (faint erythema); essentially flat with possible trace induration; no ulceration present.
2	Mild	Mild inflammation (pink color) and/or slight induration; no ulceration present.
3	Moderate	Marked inflammation (dark pink, yellow-orange color) and/or moderate induration; no ulceration present.
4	Severe	Intense inflammation (red or orange color) and/or severe induration and/or 1-2 shallow ulcerations present, but underlying structures (muscle, bone) NOT visible.
5	Very Severe	Very intense inflammation (bright red/purple or deep orange color) and/or very severe induration and/or any deep ulceration present with underlying structures (muscle, bone) visible and/or more than 2 ulcerations.

**Table 4: IGA:NL Damage** 

Score	Definition	Description
0	Absent	None

Score	Definition	Description
1	Dyspigmentation	Post-inflammatory hypo- or hyper- pigmentation
2	Scarring	Post-inflammatory scarring, including atrophic plaques

#### 14.1.2. Necrobiosis Lipoidica Color and Ulcer Scale (NLCUS)

A tool called the Necrobiosis Lipoidica Color and Ulcer Scale (NLCUS) is also under development that separately assesses the color and ulcer of NL lesions. This tool includes domains to separately assess the color/inflammation (Table 5) and induration (Table 6) of NL lesions and the extent of ulceration, if present (Table 7). The scale was developed among 4 dermatologists with expertise in granulomatous disorders, NL, and ulcers, and has face validity and has performed well in limited pre-clinical testing. Further validation of the scale is ongoing.

Instructions: Select (1) a numeric score that describes the color and (2) a numeric score that describes the ulceration status of the reference lesion\*. (\*Reference lesion is the most severely affected lesion.)

**Table 5:** NLCUS: Color/Inflammation

Score	Color/Inflammation
0	None
1	Minimal inflammation (faint erythema)
2	Mild inflammation (pink)
3	Marked inflammation (dark pink/red, orange)
4	Intense inflammation (bright red/purple, deep orange)

**Table 6: NLCUS: Induration** 

Score	Induration
0	None
1	Essentially flat with possible trace induration
2	Slight but definite induration
3	Moderate induration
4	Severe induration

Table 7: NLCUS: Ulcer

Score	Ulcer
0	None
1	1-2 shallow ulcerations, but underlying structures (muscle, bone) NOT visible.
2	Any deep ulceration with underlying structures (muscle, bone) visible and/or more than 2 ulcerations

### 14.1.3. Physician Global Assessment (PGA)

The physician's global assessment will be performed using a 10 cm VAS ranging from "none" to "extreme activity", after the question "Based on your assessment of the disease activity, draw a vertical mark (|) through the horizontal line for the level of disease activity that is present today."

#### 14.1.4. Lesion/ulcer surface area

Surface area of the lesions(s)/ulcer will be measured by the Investigator and by photography. Lesion surface area is defined as the surface area of the lesion with active inflammation/erythema. The total lesion surface area (if more than one lesion is present), the reference lesion (defined as the lesion with the highest disease severity) surface area, reference ulcer surface area (defined as the ulcer with the highest disease severity within the reference lesion), and total ulcer surface area will be calculated. The longest length and width (measured perpendicular to the longest length) measurements taken by the Investigator with a ruler will be entered into the eCRF along with an assessment of the shape of the lesion (rectangular, circular, triangular, or elliptical).

Using the digital photograph/3D scan of the lesion, the Investigator will also electronically trace the perimeter of the reference lesion and reference ulcer (if present). Based on the tracing, the surface area of the reference lesion and the surface area and volume of the reference ulcer (if present) will be calculated.

#### 14.1.5. Dermatology Quality of Life Index (DLQI)

The Dermatology Quality of Life Index (DLQI) is a self-administered, standard health-related quality of life (HRQL) instrument used in clinical trials related to skin diseases (Both, 2007). The DLQI consists of 10 items and covers six domains including: symptoms and feelings, daily activities, leisure, work and school, personal relationships, and treatment. Scores range from 0 to 30 with higher scores indicating poorer HRQL.

#### 14.1.6. Skindex-29

Skindex-29 is another self-administered standard HRQL instrument that has been proposed to be comprehensive, but less used in clinical trials (Chren, 2012). It includes 29-items with 3 domains, symptoms, emotions and functioning. Each domain is scored from 0 to 100 with higher scores indicating lower quality of life. The domains can be combined and scored separately.

### 14.1.7. Patient Global Assessment (PtGA)

The patient's global assessment will be performed using a 10 cm VAS ranging from "very severe" to "not at all", after the question "Please indicate with a vertical mark (|) on the horizontal line, how does your skin condition affect you today?"

#### 14.1.8. Exploratory Efficacy Variables in Ulcerated Patients

#### 14.1.8.1. Closure of reference ulcer

Closure of reference ulcer is defined as skin re-epithelialization without drainage or dressing requirements confirmed at two consecutive study visits 2 weeks apart.

#### **14.1.8.2.** Ulcer volume

Ulcer volume will be assessed using via the use of a 3D-imaging system.

#### 14.2. Biomarkers

Selected serum biomarkers related to the potential anti-inflammatory and/or immunosuppressive effects of PCS499 on NL will be measured. These include TNF- $\alpha$ , IFN- $\gamma$ , IL-1 $\beta$ , IL-6, IL-12, IL-17 and MCP-1.

Additionally, an association between underlying autoimmunity and the development of NL has been suggested based on the higher than expected prevalence of the disease in patients with Type 1 diabetes (as compared to Type 2 diabetes) (Erfurt-Berge, 2015). C-peptide levels will be measured to assess whether there is any benefit of PCS499 in maintaining natural insulin production.

#### 15. ASSESSMENT OF SAFETY

The safety parameters collected will include adverse events, vital signs, ECGs, physical examinations, and laboratory tests. In addition, concomitant medications will be recorded.

Date: 02 November 2018

### 15.1. Safety Parameters

### 15.1.1. Vital Signs, Height, Weight, and Body Mass Index

Vital signs, including blood pressure, heart rate, respiratory rate, and oral temperature, will be measured. Height, weight and body mass index measurements will be collected at Screening only. Vital signs will be performed after the patient has been seated for at least 5 minutes.

#### 15.1.2. Physical Examination

Full physical examinations will be performed. All abnormal findings will be documented in the eCRF.

#### 15.1.3. Electrocardiogram

Standard resting 12-lead ECGs will be performed; ECGs will be performed after the patient has rested for at least 5 minutes.

### 15.1.4. Clinical Laboratory Assessments

Clinical Safety Laboratory assessments will include hematology, chemistry and urinalysis, coagulation, and HgbA1c.

Screening panels will include virus serology (HIV, and hepatitis B and C). Results must be available prior to dosing.

The list of clinical laboratory assessments is included in Appendix A.

#### 15.1.4.1. Pregnancy Testing

PCS499 should not be administered to pregnant women. Effective methods of birth control must be used by WOCBP.

A serum  $\beta$ -HCG will be performed at Visit 1 (Screening). All WOCBP will have local urine pregnancy tests as indicated in the Schedule of Events (Table 2). A positive urine pregnancy test requires immediate interruption of study treatment until a serum  $\beta$ -HCG is performed and found to be negative. If positive, the subject must be discontinued from the study.

#### 15.1.5. Concomitant Medications

Concomitant medications are defined as any medication taken by the patient during the course of the study following the first dose. Prior medications are defined as any medication taken by the patient within 30 days of their first dose of study medication. Prior and concomitant medications will be coded using the WHO Drug Dictionary.

### 15.2. Adverse Events and Reporting Procedures

#### 15.2.1. Adverse Event Definition and Collection

An adverse event is any untoward medical occurrence in a patient administered a pharmaceutical product whether or not considered drug-related. Adverse events may include safety findings considered to be clinically significant by the Investigator, Sponsor, or Medical Monitor. An adverse event can therefore be any unfavorable and unintended sign (including an abnormal laboratory finding), symptom, or disease temporally associated with the use of a medicinal product, whether or not it is related to the medicinal product. Reporting an adverse event does not necessarily reflect a conclusion by the Investigator, Sponsor or Food and Drug Administration (FDA) that the event is causally related to the drug.

All adverse events should be captured and must be reported on the Adverse Event eCRF. Adverse events should be spontaneously reported or elicited by non-suggestive probing. All adverse event reports should contain the date the adverse event occurred, a brief description of the event (if the event consists of a cluster of signs and symptoms, record a diagnosis rather than each sign and symptom), onset date, the severity, the Investigator's assessment of the relationship to study drug, the study drug action taken, the outcome, date resolved, and whether or not the event was serious (and if so, why).

New information regarding signs and symptoms that occurred during the Screening phase and prior to the day of the first study medication dose on Day 1 of study that are related to screening procedures should be recorded on the Adverse Event log. Intercurrent illnesses or injuries should be regarded as AEs. Abnormal results of laboratory tests or diagnostic procedures are considered to be AEs if the abnormality:

- Is associated with clinical signs or symptoms
- Is considered by the Investigator to be of clinical significance
- Results in study withdrawal
- Fulfills any of the criteria for an SAE, as described in this section
- Requires intervention or further evaluation to determine the etiology of the abnormality and/or assess the risk to the patient
- Requires treatment

#### 15.2.2. Categorizing Adverse Events in Relation to Study Phase

The relationship of each adverse event must be recorded on the Adverse Event eCRF as one of the choices provided on the scale that follows, where the temporal sequence is defined as an association between administration of a drug and the observed reaction or event such that the drug was present prior to the reaction or event:

The Investigator assesses the relationship between the AE and the study drug by using the following definitions:

- DEFINITELY RELATED Onset of the event as relative to administration of the study drug is reasonable and there is no other cause to explain the event; or a rechallenge (if feasible) is positive.
- PROBABLY RELATED Onset of the event as relative to administration of the study drug is reasonable and is more likely explained by the drug than by any other cause.
- POSSIBLY RELATED Onset of the event as relative to administration of the study drug is reasonable; however, the event could have been due to another, equally likely, cause.
- UNLIKELY TO BE RELATED Onset of the event as relative to administration of the study drug, is possible but another cause itself can explain the occurrence of the event or there are no reasonable grounds for suspecting that the product could have caused the event.
- NOT RELATED Onset of the event as relative to administration of the study drug, is not reasonable; or, another cause itself can explain the occurrence of the event.

All AEs (regardless of seriousness or relationship to study drug) including those from the time of signing of the Informed Consent Form (ICF) through to the follow-up/early withdrawal visit are to be recorded in the patient's source documents and on the corresponding page(s) in the eCRF. Whenever possible, symptoms, signs, and laboratory abnormalities should be grouped as a single syndrome or diagnosis. The Investigator should specify the date of onset, intensity, action taken with respect to study drug, corrective treatment/therapy given, outcome and his/her opinion as to whether there is a reasonable possibility that the AE was caused by the study drug. All medications administered to treat an AE must be recorded in the patient's source documentation and documented in the eCRF.

#### **15.2.3.** Assigning Severity to Adverse Events

The severity of each adverse event must be recorded on the Adverse Event eCRF as one of the choices provided on the scale below:

- MILD: Awareness of sign or symptom, but easily tolerated.
- MODERATE: Discomfort enough to cause interference with usual activity.
- SEVERE: Incapacitating with inability to work or do usual activity.

#### 15.2.4. Serious Adverse Event Definition and Collection

An adverse event is considered a serious adverse event (SAE) if, in the view of either the investigator or sponsor, it includes any untoward medical occurrence at any dose that:

- Results in death
- Is life threatening
- Requires inpatient hospitalization or prolongation of existing hospitalization

- Date: 02 November 2018
- Results in a significant, persistent or permanent change, impairment, damage or disruption in the patient's body function/structure, physical activities and/or quality of life.
- Results in a congenital anomaly/birth defect
- Is a medically important event that may jeopardize the patient or may require medical or surgical intervention to prevent one of the other outcomes listed above.

The term "life threatening" in the definition of "serious" refers to an event in which the patient in the view of either the Investigator or Sponsor, was at risk of immediate death at the time of the event; it does not refer to an event that hypothetically might have caused death if it were more severe. Death is an outcome of an event. The event that resulted in death should be recorded and reported on the SAE form and documented in the eCRF.

Reporting serious adverse events to the Medical Monitor requires additional detailed reports and follow-up, depending upon the Investigator's (or in some cases the Sponsor's) estimate of a causal relationship between the test agent and the adverse event(s), and whether the adverse event(s) is identified in nature, severity, and frequency in the Investigator's Brochure or other risk information supplied to the Investigator.

In the event of a serious adverse event, the Investigator must notify the Medical Monitor immediately (within 24 hours). The SAE hotline telephone and SAE fax line numbers will be provided to each site and will be present also on the Serious Adverse Event Worksheet. Details of the serious adverse event must be documented on the Serious Adverse Event Worksheet by the site and faxed to the SAE fax line. The initial report should be as complete as possible. Information not available at the time of the initial report (e.g., an end date for the adverse event or discharge summary/testing/laboratory values received after the first report), must be documented on a follow-up Serious Adverse Event Worksheet. Sites must make an effort to obtain all hospital medical records including discharge summary confirming final diagnosis.

All serious adverse events (SAEs) should be submitted to the Institutional Review Board (IRB) as per the requirements of the IRB. The death of a patient must be immediately (within 24 hours of site awareness) reported to the IRB. All serious and non-serious adverse events should be thoroughly documented on the Adverse Event eCRF and followed out by the Investigator until the event resolves or until the termination visit. The event may be followed longer, if deemed necessary. Sites must ensure that the final SAE Worksheet captures the same information as the Adverse Event eCRF. For any death occurring during the trial, the medical condition that led to the death on the Adverse Event eCRF and also reported on the SAE Worksheet. The "outcome" status should be noted as "death" in these cases of SAEs that resulted in death. In addition, all SAEs that occur within 30 days after the last dose of study drug should be recorded and reported as noted previously.

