#### Timing of Analyses:

All endpoints will be analyzed after the last patient completes the 3-month visit and the 6-month visit (primary). A final lock of the database and the final analyses will occur after the last patient completes the 12-month visit.

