### 9.2.4. Schedule of Events

Table 2 provides detail on the schedule of assessments.

Table 2: Schedule of Events (Study PCS499-NL01)

Procedure	Screening	Dosing	Visit 3	Visit 4	Visit 5	Visit 6	Visit 7	Visit 8	Visit 9	Visit 10	Extension P	eriod
	(-28 to -1 days)	Visit 2 Day 0 (Baseline Visit)	Week 1 Day 7 (±1 day)	Week 2 Day 14 (±1 day)	Month 1 Day 28 (±3 days)	Month 2 Day 60 (±7 days)	Month 3 Day 90 (±7 days)	Month 4 Day 120 (±7 days)	Month 5 Day 150 (±7 days)	Month 6 Day 180 (±7 days)	Visit 11 Month 9 Day 270 (±10 days)	Visit 12 Month 12/ET Day 360 (±10 days)
PI/informed consent	•											
Demographic information	•											
Medical history	•											
Inclusion/ exclusion criteria	•	•										
Screening Laboratory Testing (Hep B/C, HIV, TB)	•											
Skin biopsy*	•*											
Medications	•	•	2	2	•	•	•	•	•	•	•	•
Vital signs	•	•			•	•	•	•	•	•	•	•
Physical exam	•	•					•			•	•	•
Skin/ulcer exam	•	•			•	•	•	•	•	•	•	•
Photograph/ 3D scan	•	•			•	•	•	•	•	•	•	•
IGA:NL	•	•			•	•	•	•	•	•	•	•
NLCUS		•			•	•	•	•	•	•	•	•
PGA		•			•	•	•	•	•	•	•	•

Protocol PCS499-NL01 Date: 02 November 2018

TIOLOCOLI CDT,	7 7 1 12 0 1								Bate.	02 110 (011)	2010	
DLQI		•			•	•	•	•	•	•	•	•
Skindex-29		•			•	•	•	•	•	•	•	•
PtGA		•			•	•	•	•	•	•	•	•
Safety check- in			*	**								
Safety Laboratory testing***	•	•			•	•	•	•	•	•	•	•
Blood for biomarkers		•			•		•			•	•	•
Pregnancy test**	•	•			•	•	•	•	•	•	•	•
ECG	•	•			•		•			•	•	•
Adverse Events	•	•	*	** **********************************	•	•	•	•	•	•	•	•
Drug Accountability					•	•	•	•	•	•	•	•
Study Drug Dispensed		•			•	•	•	•	•	•	•	
Study Drug Instructions	•	•										

\*If no previous history of biopsy, no biopsy within the previous 5 years, a biopsy that is not confirmed to be NL, or newly active lesion.

\*\*For WOCBP: Serum β-HCG at Screening; Urine pregnancy test at subsequent visits.

\*\*\* Additional hematology (PT, aPTT and INR) will be tested at every visit except Screening. HbA1c will be tested at Day 0 and Months 3, 6, 9 and 12.

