#### 16. ENDPOINTS

### 16.1. Primary Safety Endpoints

- Evaluation of AEs/SAEs (by type, severity, and relatedness) at each visit.
- Changes in safety clinical laboratory testing, vital signs at each visit.
- Changes in ECGs at Months 1, 3, 6, 9, and 12.

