### **2.9.1. Adverse Events**

Adverse events (AEs) will be coded using the Medical Dictionary for Regulatory Activities (MedDRA) version 21.1.

AEs occurring on or before Visit 2/Day 0 (Baseline) prior to drug administration will be regarded as “pre-treatment” and will not be included in the treatment emergent AE tabulations.

Treatment Emergent Adverse Events (TEAEs) are defined as any AE that starts or increases in severity after drug administration at Visit 2/Day 0 and will be summarized.

Listings of all AEs will be provided and separately by:

- Treatment Emergent AEs
- AEs leading to discontinuation of study
- Serious AEs

An overall summary table will be provided showing the number and percentage of patients with any:

- Pre-Treatment AEs
- TEAE
- Severe TEAE
- Serious TEAE
- Drug-related TEAE
- Drug-related severe TEAE
- Drug-related serious TEAE
- TEAE leading to withdrawal of study drug
- TEAE leading to change in study drug dose
- TEAE with outcome death

The number of reported AEs will also be shown in this summary table.

Summary tables for the following will also be presented:

- Summary of TEAEs by Body System and Preferred term,

- Summary of TEAEs by Severity,
  - If a patient has reported the same treatment emergent adverse event multiple times then the adverse event with the highest severity will be summarized.
- Summary of Drug-related TEAEs, and
- Summary of Drug-related TEAEs by Severity.
  - If a patient has reported the same drug-related treatment emergent adverse event multiple times, then the adverse event with the highest severity will be summarized.

Inferential statistical analysis comparing the AE data between active and placebo is not planned.

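### SAEs are to be recorded for 30 days after the last dose, but no contact is scheduled after Month 12/ET and the final lock may come before that window closes

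*Protocol*

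**What the plan says.** Four parts of the protocol bear on how long safety events are collected.

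- **SAE window.** Section 15.2.4 states that "all SAEs that occur within 30 days after the last dose of study drug should be recorded" and reported.
- **End of collection for all AEs.** Section 15.2.2 has every AE collected from consent "through to the follow-up/early withdrawal visit". Section 15.2.4 has known events "followed out by the Investigator until the event resolves or until the termination visit", or longer if judged necessary.
- **Schedule.** The last column of Table 2 in Section 9.2.4 is headed "Visit 12 Month 12/ET Day 360 (±10 days". Sections 9.2.3.2 and 9.2.3.3, which describe the Month 12 and early discontinuation visits, add no later contact.
- **Analysis timing.** The synopsis says "All endpoints will be analyzed after the last patient completes the 3-month visit and the 6-month visit (primary"). The synopsis and Section 17 both place the final lock and final analyses after the last patient's 12-month visit.

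The first primary safety endpoint in Section 16.1 is "Evaluation of AEs/SAEs (by type, severity, and relatedness) at each visit". SAP Section 2.9.1 defines a treatment-emergent AE as "any AE that starts or increases in severity after drug administration at Visit 2/Day 0". That definition has a start and no end.

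**The concern.** The protocol sets a fixed 30-day obligation and then provides no scheduled occasion on which to meet it. A patient who takes the drug up to the Month 12 visit and has an SAE 20 days later has no further visit or call at which anyone would ask. The event enters the database only if the patient or another clinician tells the site. The one passage that seems to promise a later visit, Section 15.2.2, names a follow-up visit that Table 2 does not contain.

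The lock timing adds to this. Nothing requires the database to stay open until the last patient's 30 days have passed. Under Section 22.3, changes after lock need joint written agreement.

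Safety is the only primary objective and the study has about 12 patients, so one patient with an SAE is 1/12 = 8.3% of the sample. A reader of the final report could not tell whether no late SAEs occurred or none were asked about.

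**Working it through.** The documents give no sample size calculation and no expected SAE rate, so there is no figure of the plan's own to reproduce. The check is a day count, followed by a range over assumed SAE rates.

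**Inputs**
- SAE window: 30 days after last dose (Protocol 15.2.4).
- Last scheduled visit: Day 360 ± 10 (Table 2).
- Month 6 visit: Day 180 ± 7; Month 9 visit: Day 270 ± 10 (Table 2).
- Patients: about 12 (Protocol 9.3).

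**Step 1: gap per patient.** With L the day of last dose and V the last scheduled visit, the days with no scheduled contact are max(0, L + 30 − V).

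| Situation | L | V | Gap (days) | Share of L + 30 |
|---|---|---|---|---|
| Dosed to Month 12 | 360 | 360 | 30 | 30/390 = 7.7% |
| Same, visit 10 days early | 350 | 350 | 30 | 30/380 = 7.9% |
| Same, visit 10 days late | 370 | 370 | 30 | 30/400 = 7.5% |
| Stops drug on Day 330 or earlier, stays on schedule | ≤ 330 | 360 | 0 | 0% |
| Stops drug on Day 345, stays on schedule | 345 | 360 | 15 | 15/375 = 4.0% |
| Stops at Month 6, still attends Months 9 and 12 | 180 | 360 | 0 | 0% |
| Stops at Month 6 and leaves the study | 180 | 180 | 30 | 30/210 = 14.3% |

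For the last row, the ± 7-day visit window gives 30/217 = 13.8% to 30/203 = 14.8%.

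**Step 2: ceiling for the study.** If all 12 patients had the full gap, 12 × 30 = 360 patient-days, or 360/365.25 = 0.99 patient-years.

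**Step 3: SAEs that could fall in the gap.** Let r be the assumed SAE rate per patient-year. Expected SAEs are 12 × r × 30/365.25. The chance that at least one of 12 patients has one is 1 − exp(−12 × r × 30/365.25).

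| Assumed r | Expected SAEs | Chance of at least one |
|---|---|---|
| 0.05 | 0.05 | 5% |
| 0.1 | 0.10 | 9% |
| 0.2 | 0.20 | 18% |
| 0.4 | 0.39 | 33% |

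These are SAEs that occur in the gap with all 12 patients affected. The number missed is smaller, because some would be reported without being asked for.

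**Step 4: lock date.** If the last patient doses to Day 360, the window runs to about Day 390. A lock permitted from Day 360 can precede its close by up to 30 days.

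**The case against.** A reader might infer that all 12 patients have 30 unobserved days and that the primary safety endpoint is under-ascertained. The documents do not support that, for these reasons.

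- **Not every patient is affected.** Section 12.5 keeps patients in the study when drug stops, and Section 10.3 has all treated patients followed on the schedule. Each clinic visit asks about events since the previous one, so most patients who stop early have their window covered.
- **Month 6 is ambiguous.** Section 9.1 makes continued dosing optional, and Section 9.2.2.8 makes only the new drug kit depend on extending. Section 10.3 intends follow-up to study termination. Patients who decline the extension may therefore still attend Months 9 and 12. The text does not settle it.
- **The primary analysis is at Month 6.** For patients who continue into the extension, the gap falls later and can touch only the final analysis.
- **Capture is passive, not absent.** Sites must record a late SAE they learn of. Section 10.3 provides monitoring after withdrawal for an AE until it settles, and Section 19.5.2 asks for reasonable efforts after refusal of treatment.
- **No counting rule is missing.** The SAP definition has no end date, so a reported late SAE already counts as treatment-emergent.
- **The follow-up visit may be loose naming** for Month 12/ET.

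All of this stands and limits the point. It does not remove it. The monitoring in Section 10.3 concerns a known event, and Section 19.5.2 sets no time or contact. Neither reaches a patient who simply completes Month 12 on drug. If the follow-up visit is only another name for Month 12/ET, it is still not a contact at 30 days.

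**Conclusion.** The point holds as a mismatch between the protocol's SAE rule, its visit schedule and its lock timing. For patients dosed up to their last scheduled visit, SAE capture over the following 30 days is passive and may be incomplete in the final safety analysis. Under-ascertainment is a risk here and has not been shown.

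The size is up to 30 of about 390 days per patient. The 360 patient-days are a ceiling that assumes 12 patients, all dosed to their last visit. Over assumed rates of 0.05 to 0.4 SAEs per patient-year, the chance of at least one SAE in the gap is 5% to 33% at that ceiling. The rates are assumptions, since the documents give none. The study is a descriptive pilot with no inferential test, so the consequence is an uncertain SAE count, not an invalid comparison.

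**What to change.** Reconcile Table 2 with Protocol Sections 15.2.2 and 15.2.4:

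1. Add one column to Table 2 for a telephone safety check-in at the end of the existing 30-day window. Use the format of the Day 7 and Day 14 calls (Section 9.2.2.2). Apply it to any patient with no later scheduled visit.
2. In Section 15.2.2, replace the reference to a follow-up visit with a contact that appears in Table 2. State whether patients who decline the extension attend Months 9 and 12.
3. In the synopsis and Section 17, hold the final lock until the last patient's 30-day window has closed.

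The counting rule in SAP Section 2.9.1 needs no change. If follow-up has already ended, the study report should say that SAE capture after the final visit was passive.

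The cost is about 12 calls by existing site staff, one column in Table 2, and a final lock up to about 30 days later. Treatment is not affected.
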